# Table 3Analysis Windows for DLCO, 6MWT, and Questionnaires
(FAS Approach)

Time point label	Target day	Interval lower bound	Interval upper bound
Baseline	1	-INF	1
Week 26	183	2	274
Week 52	365	275	449
Week 76	533	450	617
Week 100	701	618	785
Week 124	869	786	953
Etc.			

Tables, figures and listings will present the analysis windows, not the site visits.

If times are collected or other information with respect to timing (e.g. before or IP intake) this information will be taken into account in addition to the dates.

Per parameter and postbaseline analysis window, the value closest to the target date will be used in analysis tables and figures. Other values will be listed only. If more than one value is located at the same distance from the target day, then the latest in time will be selected. If there are two values on the same day and no time indicating which one is last, the average of the two will be calculated.

In addition to the predose measurements, electrocardiogram (ECGs) and the are also taken 2-3 hours postdose on selected visits (Day 1, Week 2, 4, 12, 34 for ECG and the above windowing, but tables will be created separately describing the pre- and postdose values at these selected visits.

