- The rate of decline in FVC will be analyzed using a random coefficient regression model (linear slope model) including sex, age, height, and stratification factor as covariates and a random intercept and slope. The treatment effect is determined by using estimated average slopes for each treatment group on the basis of the treatment*time interaction term from the above mixed model, with time as a continuous factor and treatment as a categorical factor. All available FVC values from baseline to Week 52 will primarily be used, including those from the ETD visit for subjects who discontinued early and do not complete their study visits up to Week 52.
- As a secondary analysis, the same model will be fit using all data until the end of the study.
- The proportion of subjects who have an absolute decline $\geq 10\%$ in %FVC at least once during the study or who die will be analyzed using logistic regression including sex, age, height, and stratum as factors using data up to Week 52.
- In addition, the same will be presented using all data up to the end of the study. A time-to-event analysis may also be used to analyze the composite endpoint of %FVC decline and mortality up to the end of the study.
- The %FVC change from baseline will be analyzed using a similar random coefficient regression model (linear slope model) as FVC in mL.

- Other spirometry endpoints will be summarized descriptively, similar to FVC.

Sensitivity analyses including multiple imputation methods and a per-protocol analysis will be performed to assess the impact of missing data, noncompliance, and protocol violations on the primary efficacy analyses. Additional exploratory analyses and graphical presentations may be performed when deemed useful to better understand the data. Details will be described in the SAP.

Time-to-event Data (Including Hospitalization, First Acute IPF Exacerbation, Mortality, and [Qualifying for] Lung Transplant), Using All Data up to the End of the Study

- Time-to-event endpoints will be graphically presented by Kaplan-Meier estimates. In addition, a Cox proportional-hazards model with terms for age, sex, height, and stratum will be used to analyze the hazard ratios for each dose compared to placebo.

Other Efficacy Endpoints

- A mixed-effects model with treatment, time (as a categorical factor), treatment*time, and baseline total score as factors in the model will be applied to the change from baseline in SGRQ total score.

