# 6.3. Algorithm of Allocating Visits to Time Analysis Windows

For the FAS analysis for efficacy, and safety endpoints, all data (including data obtained at unscheduled visits) will be placed into time analysis windows according to their relative day in the study, using to the following allocation tables (Table 2 to Table 4).

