# Table 2Analysis Windows for Efficacy and Safety Endpoints Recorded at All Time
points (FAS and PP Approach)

Time point label	Target day	Interval lower bound	Interval upper bound
Baseline	1	-INF	1

Time point label	Target day	Interval lower bound	Interval upper bound
Week 2	15	2	21
Week 4	29	22	43
Week 8	57	44	71
Week 12	85	72	106
Week 18	127	107	154
Week 26	183	155	211
Week 34	239	212	267
Week 42	295	268	330
Week 52	365	331	407
Week 64	449	408	491
Week 76	533	492	575
Week 88	617	576	659
Week 100	701	660	743
Week 112	785	744	827
Week 124	869	828	911
Week 136	953	912	995
Etc.			

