# 9.3.2.1. Primary Endpoint: Rate of Decline in FVC over a Period of 52 Weeks

The primary endpoint of annual rate of decline in FVC at Week 52 (in mL) will be analyzed, including data up to and including the 52-week analysis window defined in Section 6.3. A random coefficient regression model (linear slope model) will be used including sex, age, height and stratification factor as covariates and a random intercept and slope. The treatment effect is determined by using estimated slopes for each treatment group on the basis of the time-by-treatment interaction term from the mixed model. All available FVC values (as defined by the analysis windows) from baseline to Week 52 will be used including FVC measurements at the follow-up visit for subjects who discontinue IP prematurely and do not complete the study visits through Week 52. The model will be fit using the SAS PROC MIXED procedure, details are in Appendix 1.

The assumptions of the model will be investigated.

The same model will be used for the pooled analysis for the integrated summary of efficacy adjusted for study. More detail will be in a separate SAP.

A similar analysis will also be provided by stratification factor (standard of care).

The percent predicted FVC will be analyzed using a similar random coefficient regression model (linear slope model) as FVC expressed in mL.

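### The SAP does not settle which early-discontinuation FVC values enter the primary slope model, and its most natural reading drops some that the protocol includes

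*SAP*

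**What the plan says.** Protocol 7.3.4 uses all available FVC values from baseline to Week 52 in a random-coefficient model with continuous time, "including those from the ETD visit for subjects who discontinued early" and do not complete their visits.

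SAP 9.3.2.1 says: "All available FVC values (as defined by the analysis windows) from baseline to Week 52 will be used", and continues: "including FVC measurements at the follow-up visit for subjects who discontinue IP prematurely". Appendix 1 repeats both elements. Its code treats time as continuous but has visit as the REPEATED factor.

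For the windows, SAP 6.3 states that "all data (including data obtained at unscheduled visits) will be placed into time analysis windows according to their relative day in the study". When a window holds several values, "the value closest to the target date will be used in analysis tables and figures. Other values will be listed only". For ties: "If more than one value is located at the same distance from the target day, then the latest in time will be selected".

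In the schedules for the period after Week 52 (Protocol 6.11.2, SAP 2.5.2), spirometry is ticked for the 12-weekly, ETD and EoST/EoSA visits but not for follow-up. Follow-up comes 4 weeks after EoST/EoSA and may be a phone call. SAP 9.1, which lists changes to the planned analyses, does not mention this difference.

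**The concern.** A model with continuous time can use several values per window, so the restriction gains nothing there. It falls mainly on subjects who stop treatment. An ETD visit can occur on any day. If it comes after the scheduled visit in its window, the scheduled value is usually nearer the target and is the one kept. For a subject who never returns, the discarded value is the last FVC before dropout.

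SAP 7.4.1 assumes data are missing at random. That assumption is easier to defend when the last observation before dropout is in the model. If FVC falls faster around discontinuation, leaving that value out could bias the slopes, and could do so differently by arm. The analyses that would have probed this (on-treatment, completers versus early discontinuers, pattern mixture) are omitted under SAP 9.1. The MMRM that remains uses the same windows. The planned summaries of distance from window target are omitted too, so the report would show little of how often this happens.

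**Working it through.** **The plan's own figure.** The documents give no share of ETD values lost. The nearest figure is Protocol Table 2, which matters only for precision. With SD 275 mL and 250 per arm, SE = 275 × √(2/250) = 24.60 mL. At 80 mL and two-sided 4%, power for 600 mg is Φ(80/24.60 − 2.054) = 88.5%. Simulating both contrasts with a shared placebo arm gives 88.8% for at least one success when the 200 mg effect is 0, as Table 2 states.

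**Which values are lost if the rule reaches the model.** Base assumptions: ETD day uniform on Days 2 to 364, scheduled visits on their Table 2 target days, no return after ETD. An ETD value is lost when its day lies after the target and inside the window. Table 2 of the SAP gives, for example, the row "Week 42 295 268 330" (label, target, lower bound, upper bound), so 330 − 295 = 35 days.

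| Window | Target | Upper bound | Days after target |
|---|---|---|---|
| Week 2 | 15 | 21 | 6 |
| Week 4 | 29 | 43 | 14 |
| Week 8 | 57 | 71 | 14 |
| Week 12 | 85 | 106 | 21 |
| Week 18 | 127 | 154 | 27 |
| Week 26 | 183 | 211 | 28 |
| Week 34 | 239 | 267 | 28 |
| Week 42 | 295 | 330 | 35 |

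The Week 52 window adds none, because an ETD before Day 365 precedes its target. The sum is 173, and 173/363 = 47.7%. Without the 8 target days, on which ETD and scheduled visit coincide, it is 173/355 = 48.7%.

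**Varying the assumptions** (simulation, except the last two lines):
- Protocol visit windows (±2 or ±4 days), no return: 43%; 40% to 43% if ETDs are weighted to earlier days.
- COVID-19 visit windows, no return: 35% to 37%.
- Half of the subjects return for scheduled visits: 63% to 66%. All return: 87% to 90%. For those who return, a later scheduled value exists, so the ETD value is not their last.
- A quarter or half of ETDs fall on a scheduled visit, no return: 0.75 × 43.3% = 32.5%, or 0.50 × 43.3% = 21.7%, of all ETD values.
- Windows only bound the data period: 0%.

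**How far the lost value lies from a kept one.** In the base case each lost value follows a kept scheduled value in the same window. A window with m days after target contributes lags 1 to m, which sum to m(m+1)/2. The mean lag is (21 + 105 + 105 + 231 + 378 + 406 + 406 + 630)/173 = 2282/173 = 13.2 days; the maximum is 35.

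**Precision.** I computed generalised least squares information for a random intercept and slope model under the base assumptions. Assumed: intercept SD 800 mL, residual SD σ of 80, 120 or 150 mL, slope SD = √(275² − 2σ²), discontinuation of 10%, 20% or 30%. With σ = 80, slope SD is 251 mL; at 30% discontinuation the SE is 24.86 mL with all values and 25.01 mL under the rule, and power at 80 mL is 87.8% against 87.4%. Over the whole grid the SE rises by 0.2% to 0.8% and power falls by 0.1 to 0.4 points.

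**The case against.** The closest-value sentence speaks of tables and figures, not of the mixed model. It reaches the model only through the parenthesis in SAP 9.3.2.1, whose main words still promise all available values. The same section also uses the Week 52 window to mark where the data period ends. On that reading nothing is lost. This stands: the one-value reading is the more natural one, given Appendix 1 and its visit-indexed code, but it is an inference. Two programmers could build different primary datasets from this text.

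Three stronger readings are tempting, and the documents do not support them.
- A reader might infer that the SAP discards half of the ETD values. The share is not in the documents. It depends on the reading above, on off-schedule timing and on no return, whereas Protocol 4.5.4 provides for discontinuation at a scheduled visit and asks subjects to keep attending.
- A reader might infer that naming the follow-up visit excludes the ETD visit. The clause is introduced by 'including', so ETD values remain among the available ones. That phrase alone removes no data.
- A reader might infer a material loss of power. The calculation shows almost none, and in the base case the dropped value trails a kept one by about 13 days on average, which also limits the scope for bias.

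Timing also counts. SAP 2.7 says that part of the study team was unblinded after the decision to terminate, so redefining the primary records now needs a documented reason.

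**Conclusion.** The visit mismatch between protocol and SAP is plain from the text and needs no assumption. The loss of ETD values is conditional. If the closest-value rule governs the slope model, roughly 35% to 50% of off-schedule ETD values from subjects who do not return would be dropped, contrary to Protocol 7.3.4. Counting ETDs that fall on scheduled visits (a quarter to half of them), the share of all ETD values is 22% to 33%. If the windows only bound the period, it is zero. The effect on precision is negligible. The possible bias has no known size or direction: it depends on how many subjects discontinue without returning and on how FVC behaves around discontinuation, and the documents give neither. The point is worth correcting because the rule is ambiguous for the primary analysis and the analyses that would test the assumption are largely gone.

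**What to change.** In SAP 9.3.2.1 and Appendix 1:
- State that the slope model uses every post-baseline, pre-bronchodilator FVC value graded acceptable or borderline acceptable, from scheduled, unscheduled, ETD and EoST/EoSA visits, before lung transplant, up to Day 407 (the upper bound of the Week 52 window), at its actual study day.
- Leave the averaged baseline in SAP 6.4 unchanged.
- Adjust the REPEATED statement so that two values may share a window. The fallback error structures need the same care.
- Replace 'follow-up visit' with 'ETD visit'.
- Keep the closest-value rule for by-visit tables and the MMRM.

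Record the change as alignment with Protocol 7.3.4 and, because of the partial unblinding, explain it in the CSR as SAP 9.1 requires for changes after unblinding. Show the result from the one-value-per-window dataset next to it. The cost is SAP text, a dataset flag, a small code change and one extra model run. No new data are needed.

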### 6.4. Definition of Baseline

For all endpoints, except spirometry, and ECG parameters, baseline is defined as the last non-missing value before the first IP administration.

For spirometry endpoints and **basis**, the average of the values before the first IP administration will be calculated to reduce variability. For spirometry, for visits 1 and 2 only results graded as "acceptable" can be used, for visit 3 results graded as both "acceptable" and "borderline acceptable" can be used.

For ECGs, the mean of the triplicate ECG values will be calculated for each individual ECG parameter. The last available mean of a triplicate before the first IP administration (i.e. excluding the postdose value on Day 1) has priority over single ECGs to become the baseline, even if these single ECGs have a later date and time than the triplicate. If no triplicate is available before the first dose, the last value(s) before start of IP will be used.

# 6.5. Definition of Last Contact and End of Study (Censoring Rules)

Since vital status information is to be collected also after subject's last visit in the study, the last contact has to be defined differently for endpoints including vital status information than for those not including vital status.

#### For endpoints including vital status:

The last contact, including vital status information is defined as the latest date collected in the electronic case report form (eCRF) from the visit dates, AE dates, concomitant treatment dates, drug intake dates or laboratory test dates, study completion date or last contact or last known alive date from the vital status form.

#### For endpoints not including vital status:

The last contact, not including mortality information is defined as the latest date collected in the eCRF from the date of death, visit dates, AE dates, concomitant treatment dates, drug intake dates or laboratory test dates, study completion date. Information from the vital status form is not to be taken into account for this calculation.

# 7. HANDLING OF DATA

### 7.1. Calculation of Descriptive Statistics

For continuous parameters, descriptive statistics will be presented when N $\geq$ 2 per group. When N=1, the observation will not be shown in the table/figure but only in the listing(s).

Descriptive statistics will include at least the following:

- the number of non-missing data points (n)
- the arithmetic mean
- the standard deviation (SD) and standard error (SE) of the arithmetic mean
- the median, minimum and maximum
- 95% confidence interval (CI) of the mean (only when requested).

### 7.2. Calculation of Percentages

For event-type data (e.g. adverse events), the denominator for calculation of percentages will be all subjects in the analysis set and analysis period. For other data (e.g. worst-case analysis of assessments, demographic data), the denominator will be all subjects with (postbaseline) data for the parameter, in the analysis set and analysis window/period. Missing values will not be included in the denominator count.

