2. INTRODUCTION

For details of GLPG1690, refer to the Investigator's Brochure (IB) (Edition 6, 28-June-2019) and any relevant updates/addenda/errata.

This clinical study will be conducted in accordance with the current International Council for Harmonisation of Technical Requirements for Pharmaceuticals for Human Use - Good Clinical Practice (ICH-GCP) Guideline E6 (see also Section 10).

Idiopathic Pulmonary Fibrosis

Idiopathic pulmonary fibrosis (IPF) is a chronic, progressive, severely debilitating, and ultimately lethal lung disease predominantly affecting elderly male smokers or ex-smokers with a median age of 65 to 70 years [5]. The disease is characterized by progressive worsening of dyspnea and lung function and is associated with a poor prognosis (i.e. median survival of 2-5 years following diagnosis) [4, 12, 14, 18, 28].

The estimated IPF prevalence ranges from 14.0 to 27.9 cases per 100,000 population in the United States and from 1.3 to 23.4 cases per 100,000 population in Europe (data from 1990-2011). The estimated IPF incidence in these studies ranges from 6.8 to 8.8 cases per 100,000 population in the United States and from 0.2 to 7.4 cases per 100,000 population in Europe [8, 22, 31, 38].

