6.5.4. Functional Exercise Capacity Testing: 6MWT

A 6MWT will be performed at the clinical study center to assess pulmonary function at the time points specified in the Schedule of Activities (Section 6.11), and according to the manual provided.

The 6MWT measures the distance that a subject can walk at his/her pace on measured, flat hard surface in a period of 6 minutes. The 6MWT has been established as the walk test of choice in cardiorespiratory diseases. The change in 6-Minute Walk Distance has been found to be highly predictive of mortality [6]. Also, the Minimal Clinical Important Difference (MCID) has been validated [21].

The 6MWT will be performed based on the ATS recommendations [1] [REDACTED]. The subject should not have a contraindication to perform the 6MWT at any visit during screening and during the treatment period. Contraindications for performing the 6MWT are provided in [Appendix 10](#).

At Visit 1, the 6MWT distance of 150 meters will have to be met to be eligible to proceed to Visit 2. The subject should not have a contraindication to perform the 6MWT ([Appendix 10](#)) or should not have a condition putting the subject at risk of falling during the test (investigator’s discretion). The use of a cane is allowed, the use of a stroller is not allowed at all for any condition. The test is performed under the usual conditions for the patient, with or without oxygen as applicable.

At Visit 2, an oxygen titration test will be performed, according to the manual description. The subject should not have a contraindication to perform the 6MWT. For the oxygen titration test, resting SpO₂ should be $\geq 88\%$ with maximum 6 L O₂/min. During the walk, SpO₂ should be $\geq 83\%$ with maximum 6 L O₂/minute or $\geq 88\%$ with 0, 2 or 4 L O₂/minute. A subject will not be eligible if these criteria are not met.

For each following visit, the subject should not have a contraindication to perform the 6MWT. At Visit 3, 6MWT will be performed before IMP intake. For all visits after Visit 3 (Visits 9 and 12, and every 24 weeks thereafter), 6MWT will be performed after IMP intake. The 6MWT will be done under the same oxygen requirements as the final result in the oxygen titration period (Visit 2).

If subjects, due to any COVID-19-related reason, cannot attend visits on site, see Section 6.1.1.

6.5.5. [REDACTED]

[REDACTED]

- [REDACTED]
- [REDACTED]
- [REDACTED]
- [REDACTED]
- [REDACTED]
- [REDACTED]

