APPENDIX 10: CONTRAINDICATIONS FOR 6MWT

Absolute contraindications:

- Unstable angina during the previous month [1]
- Myocardial infarction during the previous month [1]
- SpO₂ measured by [REDACTED] <88% after 10 minutes of rest of breathing room air or at baseline oxygen flow rate [6]

Relative contraindications [1]:

- Resting heart rate >120 beats per minute
- SBP >180 mmHg
- DBP >100 mmHg

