#### 7.4. Handling of Missing Data

#### 7.4.1. Primary Approach

As the primary approach, there will be no imputation of missing values and missing values will be excluded from analyses and data is assumed to be missing at random (MAR). Missing data resulting from stopping the study is assumed to be missing completely at random (MCAR).

Missing data/visits due to the study conduct being affected by the COVID-19 pandemic (e.g. lockdown rules) can be considered MAR.

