A mixed-effects model with treatment, time (as a categorical factor defined by the analysis windows in Section 6.3), treatment\*time, and baseline total score as factors in the model will be applied to the SGRQ total score change from baseline. LS means (with 95% CI) will be estimated from the model at each time point for each treatment group as well as the differences from placebo in LS means (and 95% CIs). This model will be used to calculate the p-values for the SGRQ total score (key secondary endpoint) to use in the multiplicity adjustment.

A patient is an SGRQ responder if his absolute change from baseline in SGRQ total score is  $\leq$  -4 points. The number (%) of SGRQ responders at each analysis time point up to the end of the study will be presented and a logistic regression will be used to analyze the data similarly as described above for FVC responders.

In addition, a cumulative incidence table and graph will be presented for absolute change from baseline in total SGRQ score per time point and worst-case up to the end of the study for the categories  $\leq$ -4,  $\leq$ -3,  $\leq$ -2,...,  $\leq$ 0, ...,  $\leq$ 2,  $\leq$ 3,  $\leq$ 4, by treatment group.

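### Subjects who have died drop out of the SGRQ responder percentage and its logistic regression instead of counting as non-responders

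*SAP*

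**What the plan says.** SAP 7.2 separates event-type data, such as adverse events, from everything else. For everything else, "the denominator will be all subjects with (postbaseline) data for the parameter, in the analysis set and analysis window/period", and it adds: "Missing values will not be included in the denominator count". SAP 7.4.1 sets the general approach: "there will be no imputation of missing values and missing values will be excluded from analyses", under a missing-at-random assumption. Data lost because the study stopped are taken as missing completely at random.

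SAP 9.3.5 defines an SGRQ responder only by the change in total score (-4 or lower). It then plans: "The number (%) of SGRQ responders at each analysis time point up to the end of the study will be presented and a logistic regression". Neither the definition nor the model mentions death. A note after the scoring rules in the same section says that missing items are left alone but missing domain and total scores are imputed. It gives no method.

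For the 6MWT, SAP 9.3.7 gives descriptive summaries of distance and change. Under SAP 7.1 these use non-missing values only. Protocol 6.5.4 states "For each following visit, the subject should not have a contraindication to perform the 6MWT", and Protocol Appendix 10 lists resting SpO2 "<88% after 10 minutes of rest of breathing room air or at baseline oxygen flow rate" among the absolute contraindications.

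The itemised list of dropped analyses in SAP 9.1 keeps both. For SGRQ it removes only the per-protocol and slope analyses, and for the 6MWT it keeps total distance.

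**The concern.** The protocol describes IPF as progressive and ultimately lethal, so some subjects will die before the later time points. A patient who has died has not had a quality-of-life response, yet the plan treats that patient as if never at risk of non-response. The responder rate then answers a question about survivors, while the objective is the effect in the subjects who were randomised. If one arm has more deaths, its denominator shrinks more and its rate can rise for that reason alone.

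The plan is also inconsistent with itself. The first key secondary endpoint (SAP 9.3.2.3) counts death as disease progression, while the SGRQ responder analysis treats it as absence. SAP section 1 records that the studies were halted because the benefit-risk profile no longer supported continuing, so an output that can improve when patients are lost deserves correction even in an abbreviated report.

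The imputation note in SAP 9.3.5 is a separate defect. Read literally it contradicts 7.4.1, and two programmers could produce different SGRQ datasets from the same plan.

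**Working it through.** **Plan figure.** There is none to reproduce. The documents give no expected SGRQ responder rate and no mortality by arm, and the power figures in Protocol 7.1 concern FVC only. Every rate below is an assumption.

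**Formulas.** Let r be responders as a share of all randomised subjects and d the share who died before the time point, ignoring other missingness.
- Rate under the plan: r / (1 − d). Odds: r / (1 − d − r).
- Rate with death as non-response: r.

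**Same response per randomised subject, r = 0.25 in both arms.**
- d = 0.10 and 0.15: 0.25/0.90 = 27.8% and 0.25/0.85 = 29.4%, a gap of 1.6 points for the arm with more deaths. Odds ratio: (0.25/0.60)/(0.25/0.65) = 1.08. With death as non-response, both arms are 25.0% and the odds ratio is 1.
- d = 0.20 and 0.26: 0.25/0.80 = 31.3% and 0.25/0.74 = 33.8%, a gap of 2.5 points.
- Equal d: the gap is 0.

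**In counts, 250 per arm.** With 50 responders in each arm and 25 against 50 deaths: 50/225 = 22.2% and 50/200 = 25.0%; odds ratio (50/150)/(50/175) = 1.17. The order can also reverse: 63/250 = 25.2% and 58/250 = 23.2% become 63/225 = 28.0% and 58/200 = 29.0%.

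**Same response among survivors instead.** Take 27.8% of survivors in both arms, with d = 0.10 and 0.15. The plan reports 27.8% in both. Per randomised subject the rates are 0.278 × 0.90 = 25.0% and 0.278 × 0.85 = 23.6%. The plan then shows no false gain, but it hides a 1.4-point disadvantage.

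**Against sampling error.** For 31.3% and 33.8% on 200 and 185 survivors, the standard error is √[0.325 × 0.675 × (1/200 + 1/185)] = 4.8 points, so 2.5 points is about half a standard error.

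**Why the denominator needs a restriction.** Protocol 4.1 expects treatment to last from 52 to about 132 weeks, and the study then stopped early. Suppose 15 of 60 subjects observed at a late visit respond (25%), and 40 subjects died earlier. Adding all 40 gives 15/100 = 15%. Some of those 40 enrolled too late for the visit to fall due before closure, while comparable living subjects stay out. Deaths would be over-weighted.

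**6MWT.** No figure in metres follows from the documents, because it would depend on the distance assigned to untested subjects.

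**The case against.** Much of the case on the other side stands.
- **Rank of the analyses.** SGRQ response is not a listed endpoint. The key secondary endpoint is change in total score, tested by the mixed model. The 6MWT is descriptive. Neither analysis is in the testing hierarchy.
- **Visibility.** Mortality by arm appears elsewhere: time to all-cause mortality (SAP 9.3.3.1), the components of the FVC-or-death composite (9.3.2.4), discontinuations and time in study (9.2.2). A reader could see an imbalance but could not correct the responder rate from those tables.
- **Conditional bias.** It needs unequal mortality, and its form depends on what is held equal between arms, as the working shows.

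Four stronger readings are tempting but not supported.
- **That subjects who become too ill leave the SGRQ.** It is collected at ETD and at EoST/EoSA, and subjects who stop treatment are asked to keep attending. The Week 52 questionnaire window (Day 275 to 449) can take in later ETD scores. Only death is clearly irrecoverable.
- **That the 6MWT excludes anyone whose lungs deteriorate.** The SpO2 rule is a specific resting threshold, and the test manual is not available here. The 6MWT has no ETD or EoST/EoSA assessment, so it is more exposed than the SGRQ, but by how much is unknown.
- **That "median survival of 2-5 years following diagnosis" gives the trial's death rate.** It describes IPF generally from diagnosis. The trial requires FVC of at least 45% and DLCO of at least 30% predicted and a 150 m walk, and it excludes recent exacerbations.
- **That an active arm actually benefited.** The documents contain no results by arm.

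**Conclusion.** The point holds for death and SGRQ response. As written, SAP 7.2, 7.4.1 and 9.3.5 remove subjects who have died from both the percentage and the regression, and nothing else in the plan puts them back. The estimand in SAP section 4 concerns FVC decline and has no strategy for death. The pattern-mixture analysis that had a category for death was for FVC only and has been dropped.

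The effect is modest. With 25% response per randomised subject, a 5- to 6-point difference in deaths moves the comparison by 1.6 to 2.5 points, and equal mortality moves it by nothing. These rates are illustrative. The affected results are supportive, and no confirmatory conclusion depends on them.

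The contradiction between 7.4.1 and the imputation note in 9.3.5 needs no assumption and must be reconciled. For the 6MWT the documents support a request for transparent counts; scoring untested subjects as 0 m is a choice, not a correction.

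**What to change.** 1. **SAP 9.3.5, with an exception in 7.2.** Count a subject who died before the time point as an SGRQ non-responder, in the percentage and in the logistic regression.
2. **Denominator.** At each time point include only subjects, living or dead, whose visit fell due before study closure, for example by first-dose date and the target day in SAP Table 3.
3. **Other missingness.** Show missing values from study closure or COVID-19 separately by arm, and do not count them as failure.
4. **Imputation.** Reconcile the note in 9.3.5 with 7.4.1: delete it, or state the method and make clear that no score is created after death.
5. **6MWT, SAP 9.3.7.** Beside the observed-case summary, show by arm and time point the number with data, dead and not tested, with the reason where already recorded. A 0 m or worst-rank summary is optional.

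**Cost.** Some SAP wording, one responder derivation with a due-date flag, and one table of counts. SAP 6.5 shows that date of death is already in the eCRF, and no new field is needed if only recorded reasons are used. SAP 2.7 says part of the team was unblinded after termination, so the change should be documented with its reason, as SAP 9.1 requires for changes after unblinding. Responder percentages will fall, possibly by more than a little at late time points.
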